### **8.2.2. Mycological outcomes**

The percentage of subjects with mycological eradication (negative culture for growth of Candida species) at Baseline, Week 12, Week 24 (TOC) and Week 36 (EOFU) visits will be analyzed based on ITT, mITT, and PP sets using the same inferential analysis employing the same methods as for the primary analysis as noted in Section 8.1.1. The subjects with missing specified visit data for the mycological outcome will be imputed as mycological persistence using the NRI method described in [Section 4.4.1](#).

Mycological outcomes will be assessed at the specified visit according to the following definitions.

- Mycological Eradication: A subject with negative culture for Candida species;
- Mycological Persistence: A subject with a positive culture for Candida species.

In addition, a sensitivity analysis will be conducted based on the ITT set where subjects with the imputed mycological outcome using the NRI method at the specified visit will be removed from the analysis.

In addition, a summary table will be presented to include MIC range, mode, MIC50, and MIC90, based on the ITT, mITT, and PP sets by treatment group and geographical region (USA or Ex-USA) for the following MIC results from 2 different methods, CLSI and EUCAST, respectively:

- MIC results for SCY-078 and fluconazole (FLU) at 24 hours against candida species isolates obtained at Week 12, Week 24 (TOC) and Week 36 (EOFU);
- MIC results for SCY-078 and fluconazole (FLU) at 48 hours against candida species isolates obtained at Week 12, Week 24 (TOC) and Week 36 (EOFU) visits.

### **8.2.3. Quality of Life Analysis**

Quality of life will be assessed at Day -14, Baseline (Day 1), Week 12, Week 24 (TOC) and Week 36 (EOFU). Quality-of-life tools will include the Euro Quol 5 Dimensions 5-Level Version (EQ-5D-5L), Short Form Health Survey (SF-36) and Female Sexual Distress-Revised Scale (FSDS).

#### **8.2.3.1. Euro Quol 5 Dimensions 5-Level Version**

The EQ-5D-5L essentially consists of 2 parts: the EQ-5D descriptive system and the EQ visual analogue scale (EQ VAS). The descriptive system comprises five dimensions: mobility, selfcare, usual activities, pain/discomfort and anxiety/depression. Each dimension has 5 levels: no problems, slight problems, moderate problems, severe problems, unable to/extreme problems. The EQ VAS records the patient's self-rated health on a scale from 0-100 where 100 is the 'best imaginable health state' and 0 is the 'worst imaginable health state'. Additionally, an EQ-5D summary index will be calculated to reflect how good or bad a health state, which is defined by

combining one level from each of the five dimensions, is according to the preferences of the general population of a country/region. The EQ-5D index value is derived by applying a formula that attaches values (weights) to each of the levels in each dimension. The index values will be selected from the value sets which can be obtained from EuroQol office, refer to [Appendix 2](#) for the samples of the value sets for this study. The value sets contain the index values for all possible EQ-5D health states for each country/region. If a standard EQ-5D-5L value set is not available for a specified country/region, it should discuss with client to select an EQ-5D-5L value set for a country/region that most closely approximates the country/region investigated. No missing dimension will be imputed.

A summary of the number and percentage of subjects by categorical responses of the 5 EQ-5D dimensions will be presented by treatment and by visit.

EQ-5D Summary Index and EQ VAS will be summarized by treatment and by visit descriptively. Change from Baseline to Week 12, Week 24 (TOC) and Week 36 (EOFU) in EQ-5D Summary Index and EQ-5D VAS will be analyzed and reported using an Mixed-Effect Model for Repeated Measure (MMRM) analysis model, using the ITT, mITT, and PP sets (one such analysis for all post-baseline data, grouped by time point), will be used to compare the difference between treatment groups. The model will include treatment group, Country, visit, uncontrolled diabetes mellitus (Yes or No) and the treatment-by-visit interaction as classification variables and the baseline value as covariate. An unstructured covariance matrix will be used. Based on this modeling, a point estimate, associate SE, 95% CI, and corresponding p-value will be provided for least squares (LS) mean treatment difference versus placebo at all scheduled timepoints. Degrees of freedom will be calculated using the Kenward-Roger procedure.

In addition, an analysis of covariance (ANCOVA) model will be used having treatment group, Country and uncontrolled diabetes mellitus (Yes or No) as classification variables, and the baseline value as the continuous covariate as a sensitivity analysis, including and excluding the imputed values as the LOCF approach described in [section 4.2](#), respectively, for change from baseline of EQ-5D Summary Index and EQ VAS and for each scheduled timepoints. For each treatment and treatment comparison versus placebo, the least squares mean, associate standard error (SE), 95% confidence interval and corresponding p-value will be presented.

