11.1 Inclusion Criteria

Subjects must fulfill all the following criteria at Screening and/or Baseline to be eligible for study admission:

1. Subject is a postmenarchal female subject 12 years and older at Screening and is in good general health based on medical history, physical examination, vital sign measurements and safety laboratory tests performed at the Screening visit and prior to administration of the initial dose of study drug.
2. Subject has a diagnosis of symptomatic VVC that meets the following criteria at Screening:
 - a. A total composite score of ≥ 4 on the VSS Scale
 - b. Positive microscopic examination with 10% KOH in a vaginal sample collected at Screening revealing yeast forms (hyphae/pseudohyphae) or budding yeasts
 - c. Normal vaginal pH (≤ 4.5)
 - d. A minimum of three episodes of VVC in the past 12 months, including the current episode, that required administration of antifungal medication. Besides the current episode, at least one of the previous episodes in the past 12 months is required to have been a physician-diagnosed episode of VVC, with at least one positive test confirming vaginal yeast infection (e.g., KOH, culture or fungal polymerase chain reaction)
3. Subject meets the following criteria at Baseline (Day 1):
 - a. Significant resolution of signs and symptoms of *Candida* infection (total composite score ≤ 2 on the VSS Scale)
 - b. Culture positive for *Candida* spp. in a vaginal sample collected at Screening
 - c. Normal vaginal pH (≤ 4.5)
4. Subject is able to take oral tablets and capsules.

5. Subject is not pregnant or lactating and is highly unlikely to become pregnant since she meets at least one of the following criteria:
 - a. Subject is a female subject who is not of reproductive potential and is eligible without requiring the use of contraception. A female subject who is not of reproductive potential is defined as one who: (1) has reached natural menopause (defined as 6 months of spontaneous amenorrhea with serum follicle-stimulating hormone levels in the postmenopausal range as determined by the local laboratory, or 12 months of spontaneous amenorrhea); (2) has undergone bilateral oophorectomy and/or hysterectomy or (3) is 3 months post bilateral tubal ligation. Spontaneous amenorrhea does not include cases for which there is an underlying disease that causes amenorrhea (e.g. anorexia nervosa).

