18.3 Subject Disposition, Discontinuation, and Baseline Data

Subject disposition in terms of the number and percentage of subjects enrolled by site will be tabulated. The number of subjects randomized, number completing the study, and reasons for discontinuation will be summarized by treatment group. Subject demographics and baseline characteristics such as age, race, ethnicity, sex, weight, height, body mass index, region (if applicable) and other relevant parameters will be tabulated by treatment group.

Baseline is defined as the last non-missing assessment prior to the date (and time if appropriate) of the first dose of study drug. Change from baseline is defined as: post-baseline value – baseline value.

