### 3.2.3. Other Secondary Endpoints:

Efficacy as measured by:

- The percentage of subjects with no Mycologically Proven Recurrence up to Week 4, Week 8, Week 12, and Week 36 (end of follow-up [EOFU]);
- The time to the first Recurrence (Mycologically Proven, Presumed or Suspected) of VVC through EOFU;
- The percentage of subjects with Mycological Eradication (negative fungal culture) at Week 12, Week 24 (TOC) and Week 36 (EOFU);
- The percentage of subjects with no Mycologically Proven, Presumed or Suspected Recurrences up to Week 4, Week 8, Week 12 and Week 36 (EOFU);
- The percentage of subjects with no Mycologically Proven or Presumed Recurrences up to Week 4, Week 8, Week 12, Week 24 (TOC) and Week 36 (EOFU);
- The proportion of subjects in four ordered categories related to the number of Recurrences (Mycologically Proven, Presumed or Suspected) of VVC from Baseline (Day 1) to Week 24 (TOC) and Week 36 (EOFU). The three categories of recurrence are defined as (i) 0 episode, (ii) 1 episode, (iii) 2 to 3 episodes, and (iv)  $\geq 4$  episodes;
- The absolute number of Mycologically Proven, Presumed or Suspected Recurrences from Baseline (Day 1) to Week 24 (TOC) and Week 36 (EOFU);
- Absolute improvement in QOL outcomes at Week 12, Week 24 (TOC) and Week 36 (EOFU) as measured by EQ-5D, SF-36 and FSDDS;

Safety and tolerability as measured by:

- Adverse events (AEs), vital signs, treatment discontinuation and safety laboratory tests.

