#### 4. General Statistical Considerations

Continuous data will be described using descriptive statistics (i.e. n, mean, standard deviation (SD), median, minimum, and maximum). Categorical data will be described using the subject count and percentage in each category. For the summary statistics of all numerical variables unless otherwise specified, minimum and maximum will be displayed to the same level of precision as reported. Mean and median will be displayed to one level of precision greater than the data collected. Standard deviation / standard error will be displayed to two levels of precision greater than the data collected. P-values will be rounded to three decimal places. If a p-value is less than 0.001 it will be reported as “<0.001.” If a p-value is greater than 0.999 it will be reported as “>0.999.” Data will be displayed in all listings sorted by treatment group.

Subjects will be identified in the listings by the subject identification number concatenated with the investigator number.

When count data are presented, the percentage will be suppressed when the count is zero in order to draw attention to the non-zero counts. A row denoted “Missing” will be included in count tabulations where specified on the shells to account for dropouts and missing values. The denominator for all percentages will be the number of subjects in that treatment within the analysis set of interest, unless otherwise specified.

Unless otherwise specified, baseline will be defined as the last non-missing assessment prior to or on the date (and time if appropriate) of the first dose of study drug. Change from baseline is defined as post-baseline value – baseline value.

The study day will be calculated as follows:

If the assessment date occurs on or after the date of the first dose of study drug:

$$\text{Study day} = \text{assessment date} - \text{first dose date} + 1.$$

If the date of interest occurs before the date of the first dose of study drug:

$$\text{Study day} = \text{assessment date} - \text{first dose date}$$

There is no study day 0.

All analyses will be conducted using SAS Version 9.3 or higher. All statistical tests will be two-sided and interpreted at a 5% significance level.

This statistical analysis plan is created for the main study. Regarding the detailed description of the statistical analysis of the nested sub-study, please refer to the [Appendix 4](#).

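### The quality-of-life models adjust for one baseline score only, leave the collected Day -14 score out, and let it stand in for a missing Day 1 score

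*SAP*

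**What the plan says.** The endpoint in SAP 3.2.3 is "Absolute improvement in QOL outcomes at Week 12, Week 24 (TOC) and Week 36 (EOFU) as measured by EQ-5D"; the FSDS and the SF-36 are the other two instruments. SAP 8.2.3 and Protocol 14.17 schedule the questionnaires at Day -14, Day 1 and Weeks 12, 24 and 36.

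SAP 8.2.3.1 models "Change from Baseline to Week 12, Week 24 (TOC) and Week 36 (EOFU) in EQ-5D Summary Index and EQ-5D VAS" by MMRM, with treatment, country, visit, uncontrolled diabetes "and the treatment-by-visit interaction as classification variables and the baseline value as covariate". The sensitivity ANCOVA also carries a single baseline covariate. Sections 8.2.3.2 and 8.2.3.3 apply the same models to SF-36 and FSDS.

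No QoL section defines its own baseline, so SAP Section 4 governs: "baseline will be defined as the last non-missing assessment prior to or on the date (and time if appropriate) of the first dose". Protocol 18.3 words the rule differently: "Baseline is defined as the last non-missing assessment prior to the date (and time if appropriate) of the first dose of study drug". SAP Section 11 does not list that difference.

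The two pre-randomisation scores come from different clinical states. Protocol 11.1 requires at Screening "A total composite score of ≥ 4 on the VSS Scale" and at Day 1 a score of 2 or less. Protocol 12.1.1 puts the first fluconazole dose after all other Day -14 procedures, so the Day -14 questionnaire reflects the untreated episode.

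**The concern.** Two things follow.

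First, a prognostic measurement is paid for and then left out of the models. How a woman's QoL stands during her own candidiasis episode plausibly says something about her later scores, beyond what her Day 1 score says. Because it is taken before randomisation, it can be adjusted for without risk of bias.

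Second, the last-non-missing rule gives a woman without a Day 1 questionnaire her acute-episode score as baseline. Her change then includes her recovery on open-label fluconazole, which has nothing to do with the randomised drug. The ANCOVA is planned to report a least squares mean for each treatment, and the FSDS shift tables are anchored to baseline, so within-arm change will be shown, under an endpoint labelled improvement. That label already fits poorly: change from a Day 1 that follows treatment response describes whether a response is kept.

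**Working it through.** **No planned figure to reproduce.** Neither document gives an effect size, SD, power or expected score for QoL.

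**1. Treatment difference.** With baseline b as covariate, regressing y - b on treatment and b gives the same treatment coefficient as regressing y on treatment and b; only the coefficient of b changes, by exactly 1. Simulated fits differ by about 3e-14 at most. Both candidate baselines precede randomisation, so neither biases the comparison.

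**2. Effect of the fallback (illustration; every input is an assumption).** 0-100 scale capped at 100, 120 women per arm, means 65 at Day -14 and 90 at Day 1, SD 15, correlation 0.5, a recurrence costing 15 points, recurrence in 35% versus 57% (the complements of the planned 65% and 43% success rates).

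Mean change from Day 1 is -4.5 (active) and -7.4 (placebo). From Day -14 it is +18.2 and +15.3. The gap is 18.2 + 4.5 = 22.7 points. If a proportion p has the fallback, mean change moves by p × 22.7, for example 0.10 × 22.7 = 2.3 points. Simulated results:

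| Day 1 missing | Mean change, active / placebo | Adjusted difference | SE |
|---|---|---|---|
| 0% | -4.5 / -7.4 | 2.9 | 1.70 |
| 5% | -3.4 / -6.3 | 2.8 | 1.73 |
| 10% | -2.3 / -5.1 | 2.9 | 1.74 |
| 20% | 0.0 / -2.8 | 2.9 | 1.76 |

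The within-arm figures drift upwards in both arms. The difference does not move beyond simulation noise, and the SE rises slightly.

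**3. Gain from adding Day -14.** If r is the partial correlation of Day -14 with the outcome given Day 1, residual variance is multiplied by 1 - r², and 240 women carry the precision of 240/(1 - r²):

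- r = 0: factor 1, equivalent to 240 women
- r = 0.2: 0.96, 240/0.96 = 250
- r = 0.3: 0.91, 240/0.91 = 264
- r = 0.4: 0.84, 240/0.84 = 286

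In the step 2 scenario with complete data, the SE falls from 1.70 to 1.63. Across assumed pairwise correlations of 0.2 to 0.7 the cut is about 1% to 5%; a repeat run gave 0.9% at 0.2, 4.2% at 0.5 and 6.1% at 0.7.

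**4. Missing covariates.** Dropping women without Day 1 scores gives SEs of 1.75, 1.79 and 1.90 at 5%, 10% and 20% missing, worse than the fallback's 1.73, 1.74 and 1.76. With 10% of each score missing, two covariates and complete cases only, the SE is 1.81 against 1.74. Filling both covariates with the pooled mean reverses this: in the repeat run the same case gave 1.65 against 1.74. With 5% to 10% of each score missing and correlations of 0.2 to 0.7, the SE is about 1% to 9% below the fallback rule; the repeat run reached just under 10% at 0.7. The treatment difference was unbiased throughout.

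**The case against.** The best reply is that Day 1 is the point of randomisation, a legitimate sole covariate, and that the objective is a comparison with placebo, which the baseline rule does not bias. That stands. It is also true that the fallback is a written rule applying unless otherwise specified, that SAP 8.2.3 labels the visit Baseline (Day 1), that no missing rate is given, and that SAP Section 11 allows other variables to be considered at blinded review. But allowing is not committing, and labelling a visit does not clearly override the general rule. The objection that a second covariate loses women holds for complete-case analysis only.

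A reader might infer more than the documents support:

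- *Every woman is near the instrument's limit on Day 1.* No Day 1 QoL score is given, and the VSS is not a QoL scale. From the SAP Appendix 3 constants the SF-36 summary maxima are 59.0 (physical) and 62.3 (mental) against a norm of 50, and nothing puts a woman with VSS 2 or less there. For FSDS the limit is a floor at 0, and nothing says that sexual distress resolves in 14 days.
- *Day -14 is wholly unused.* The by-visit summaries do not list their visits and may include it.
- *A woman in full EQ-5D health has at least 1.000 - 0.876 = 0.124 to lose.* SAP Appendix 2 prints part of a value set, US column only, stopping at state 11141. States such as 11211 or 21111 are not shown and could lie above 0.876.
- *Improvement should be headlined as change from Day -14.* That would credit open-label fluconazole to both arms; in the illustration, placebo would improve by 15.3 points.

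**Conclusion.** The point holds as a modest gap in specification and a missed gain in efficiency, confined to secondary endpoints. The documents establish that the QoL models use one baseline covariate, that Day -14 enters no planned inferential analysis, and that the general rule substitutes it for a missing Day 1 score without a QoL-specific restriction. The substitution inflates within-arm change in proportion to the share missing and costs about 2% to 4% in SE at 5% to 20% missing in the illustration (1.73/1.70 to 1.76/1.70). It does not bias ibrexafungerp against placebo.

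The gain from adding Day -14 rests on a partial correlation that the documents do not give: nothing near 0, and 4% to 16% of residual variance at 0.2 to 0.4. The simulated figures rest on assumed means, SD, correlations and recurrence effect, and on a single-visit ANCOVA rather than the full MMRM.

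**What to change.** Before unblinding, amend SAP 8.2.3.1 to 8.2.3.3:

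1. Add the Day -14 score of the same instrument as a second continuous covariate in the MMRM and ANCOVA.
2. Define QoL baseline as the pre-dose Day 1 questionnaire, with no Day -14 substitution. Reconcile the baseline wording of Protocol 18.3 and SAP Section 4, and list the difference in SAP Section 11.
3. Fill a missing Day 1 or Day -14 covariate with the mean over both arms combined, without reference to treatment or outcome, so that missing covariates remove no randomised woman. For a woman without a Day 1 score, fit the observed visit score, or subtract the same imputed value; by step 1 of the working the treatment difference is the same. Limit descriptive change tables to women with an observed Day 1 score.
4. Describe change from Day 1 as change or maintenance after fluconazole response, and state that Day -14 scores are shown descriptively only.

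The cost is SAP text, one degree of freedom per model and a simple imputation step. No new data are needed, and the primary and key secondary analyses are untouched.

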#### **8.2.3.2. Short Form Health Survey**

A score will be calculated for each of the 8 scales in SF-36. Each scale score ranges from 0 to 100, with higher score reflecting less disability. The partially missing scores may be imputed as described in [Appendix 3](#) and used in the summary and analysis. 2 overall scores will be further derived: Physical Component Summary score (PCS) and Mental Component Summary score (MCS). The summary scores range from 0 to 100, with higher scores indicating better levels of function and/or better health. See scoring algorithm in [Appendix 3](#). All 8 scale scores and 2 overall scores will be summarized by visit. Change from Baseline in scale scores, PCS, and MCS will be analyzed and reported using the same MMRM and ANCOVA model as specified for the change in EQ-5D Summary Index in [Section 8.2.3.1](#).

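### The quality-of-life MMRM fits one baseline slope to Weeks 12, 24 and 36; adding baseline-by-visit would guard against a small, conditional loss of precision at almost no cost

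*SAP*

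**What the plan says.** SAP 8.2.3.1 analyses "Change from Baseline to Week 12, Week 24 (TOC) and Week 36 (EOFU) in EQ-5D Summary Index and EQ-5D VAS" by MMRM. On the fixed effects it states: "The model will include treatment group, Country, visit, uncontrolled diabetes mellitus (Yes or No) and the treatment-by-visit interaction as classification variables". The sentence closes with "the treatment-by-visit interaction as classification variables and the baseline value as covariate", so baseline is added as a covariate with no interaction. On the covariance it states: "An unstructured covariance matrix will be used".

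The same section plans an ANCOVA with "the baseline value as the continuous covariate as a sensitivity analysis, including and excluding the imputed values as the LOCF approach", fitted "for change from baseline of EQ-5D Summary Index and EQ VAS and for each scheduled timepoints". Because it is fitted visit by visit, the ANCOVA estimates a separate baseline slope at each visit.

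For the SF-36, SAP 8.2.3.2 says the changes "will be analyzed and reported using the same MMRM and ANCOVA model as specified for the change in EQ-5D Summary Index". SAP 8.2.3.3 does the same for the FSDS total. The model therefore serves 2 EQ-5D scores (index and VAS), 10 SF-36 scores (8 scales, PCS and MCS) and 1 FSDS score, 13 in all.

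SAP 11 explains that MMRM and ANCOVA replaced the protocol's two-way ANOVA so that baseline could be accounted for. It leaves room for further variables at blinded data review.

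**The concern.** The model lets the treatment effect differ by visit and leaves the covariance free, yet holds constant over time the effect of baseline, the one continuous covariate. A common slope is an extra assumption that the rest of the model does not need.

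There is a reason to doubt it here. Baseline is Day 1, just after open-label fluconazole, in women selected for a VSS score of 2 or less (protocol 11.1). The last dose is at Week 20 (protocol 12.1.2), and Week 36 closes a follow-up period without study drug. The relation of the score to Day 1 could well differ between Week 12 and Week 36.

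If it does, the pooled slope is wrong at one or more visits, residual variance there is larger than it need be, and the interval for the treatment difference is wider. The by-visit ANCOVA relaxes the slope, but only as a sensitivity analysis, with LOCF values or without imputed values. No planned analysis combines visit-specific slopes with likelihood-based handling of missed visits.

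**Working it through.** **Inputs from the documents.** About 240 women randomised 1:1, so n = 120 per arm (protocol 18.1, SAP 4.1); post-baseline visits at Weeks 12, 24 and 36; model terms as above. The documents state no SD, correlation, slope or power for any quality-of-life score, so there is no figure of the plan's own to reproduce on this point. The sample size does reproduce (exact power of Fisher's test at 120 per arm for 65% v 43% is 0.909), but it concerns the primary binary endpoint only.

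**Assumed inputs.** Correlations of the Day 1 score with each later score, correlations among the later scores, and SD 1 at every visit unless stated.

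**Formulas.** Let b_t be the slope of the score at visit t on baseline, s_t² the residual variance around that slope, σ² the baseline variance, and b the common slope to which the likelihood fit converges. Using change instead of the score subtracts 1 from every slope and alters nothing below. With complete data, the variance of the treatment difference at visit t is:

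- visit-specific slopes: (2/n) s_t²
- common slope: (2/n) [s_t² + (b_t − b)² σ²]

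The SE ratio is therefore √[1 + (b_t − b)² σ² / s_t²]. The common slope is the generalised-least-squares average b = (1′Ω⁻¹β)/(1′Ω⁻¹1), where β holds the three b_t and Ω is the fitted covariance including the slope error; it is solved by iteration. With unit SDs, b_t is the correlation and s_t² = 1 − b_t².

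**Steep decline, 0.7/0.5/0.3** (later visits correlated 0.7 if adjacent, 0.5 between Weeks 12 and 36). The pooled slope is b = 0.595. At Week 36 the slope error is 0.595 − 0.3 = 0.295, its square 0.087, and s² = 1 − 0.09 = 0.91. The variance ratio is 1 + 0.087/0.91 = 1.096 and the SE ratio 1.047. Relative efficiency at Weeks 12, 24 and 36 is 0.979, 0.988 and 0.913; at Week 36, 240 women act like 240 × 0.913 = 219.

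**Moderate decline, 0.6/0.5/0.4.** b = 0.523. At Week 36 the error is 0.123, its square 0.0152, and s² = 0.84. The variance ratio is 1.018 and the SE ratio 1.009.

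**Other patterns.** Excess SE of the common-slope model:

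| Correlation with Day 1 (W12/W24/W36) | Assumed later correlations (12–24/12–36/24–36) | W12 | W24 | W36 |
|---|---|---|---|---|
| 0.5/0.5/0.5 | 0.6/0.6/0.6 | 0% | 0% | 0% |
| 0.60/0.55/0.50 | 0.65/0.60/0.65 | 0.1% | 0.0% | 0.2% |
| 0.6/0.5/0.4 | 0.65/0.55/0.65 | 0.5% | 0.0% | 0.9% |
| 0.70/0.49/0.343 (AR(1)) | 0.70/0.49/0.70 | 1.1% | 0.7% | 3.5% |
| 0.7/0.5/0.3 | 0.60/0.45/0.60 | 1.3% | 0.5% | 4.4% |
| 0.7/0.5/0.3 | 0.70/0.50/0.70 | 1.1% | 0.6% | 4.7% |
| 0.6/0.4/0.6 | 0.6/0.6/0.6 | 0.1% | 1.7% | 0.1% |
| 0.4/0.5/0.6 | 0.60/0.55/0.65 | 0.9% | 0.0% | 0.5% |

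The result also moves with the later correlations. Taking 0.7/0.7/0.5 in the steep case gives b = 0.630 and √(1 + 0.330²/0.91) = 1.058, a 5.8% excess at Week 36. That pattern, however, ties Week 36 more closely to Week 12 than to Week 24.

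**Simulation check** (N = 240, 1,500 runs, no treatment effect, complete data). For 0.6/0.5/0.4 the Week 36 SE ratio was 1.005; for 0.7/0.5/0.3 it was 1.053. Bias was within Monte Carlo error at every visit for both models.

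**The case against.** The strongest reply is that a common slope is a valid, parsimonious choice and that nothing in the documents shows it to be false. This stands. A reader might infer that baseline is wrongly adjusted at the later visits and that precision is lost chiefly at Week 36. Neither follows. The loss is zero if slopes are equal, and it is greatest at Week 24 for 0.6/0.4/0.6 and at Week 12 for 0.4/0.5/0.6. Falling correlation is not enough either, because the slope is the correlation times the SD ratio. Correlations of 0.6/0.5/0.4 with SD ratios of 1.0/1.2/1.5 give 0.6 × 1.0 = 0.5 × 1.2 = 0.4 × 1.5 = 0.6, and no loss. Later SDs could indeed exceed the Day 1 SD, since every woman is resolved at Day 1.

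A reader might also count chance baseline imbalance as a second harm. It is the same one. With slope error 0.295, the excess variance (2/120) × 0.087 is exactly the variance of the part of a random baseline difference left uncorrected.

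Nor do the documents support calling the treatment difference biased. With complete data it is not. In simulations with missing-at-random dropout that depended on baseline differently by arm, the common slope gave a bias of 0.02 to 0.05 SD at Week 36, which the interaction removed. That dropout model is an assumption, and the documents give no basis for expecting it.

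Finally, the by-visit ANCOVA already allows separate slopes, and relaxing an assumption is a proper use of a sensitivity analysis. This is partly right: it is a useful check, but it gives up the likelihood handling of missed visits. If it disagreed with the MMRM, the slope and the missing-data method could not readily be told apart.

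**Conclusion.** The model as written imposes one baseline slope on three visits for 13 scores. If the slopes differ, efficiency is lost. With complete data and equal SDs, the standard error is larger by nothing under equal slopes, by about 1% or less at any visit under moderate decline, and by roughly 3.5 to 5% at Week 36 under steep decline. Every correlation behind these figures is assumed. These are other secondary endpoints with no stated power, and neither the primary nor the key secondary analysis uses the model. The point is minor, but the improvement is nearly free and worth prespecifying.

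**What to change.** In SAP 8.2.3.1, add the baseline-by-visit interaction to the MMRM fixed effects. SAP 8.2.3.2 and 8.2.3.3 inherit it by cross-reference. Leave the other terms, the unstructured covariance and the Kenward-Roger degrees of freedom as they are, and keep the by-visit ANCOVA as the sensitivity analysis. State the term in the SAP itself instead of relying on the allowance in SAP 11 for variables added at blinded review.

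The cost is three slopes in place of one, so 2 degrees of freedom per model, with no new data and negligible loss if the slopes turn out equal. MMRM and ANCOVA would then adjust for baseline in the same way, so a disagreement between them would point mainly to the handling of missed visits (Country and diabetes effects would still be common across visits in the MMRM).
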